2. **Describe any benefit to the population from which the subject is drawn:** Future patients may also have less discomfort and less anxiety during peripheral intravenous cannulation. Also, future health care providers may have less risk of accidental needle stick injury because of the finding of this study. or N/A

3. **Describe any benefit to science, society, and humanity in general:** Adult patients may be more comfortable during peripheral intravenous cannulation in the future. There may also be fewer accidental needle stick injuries in the future. Furthermore, the findings of this study could help save some healthcare money and decrease the environmental pollution problem. or N/A

B.4 Alternatives

1. **Describe alternatives to participating in this research study (e.g. to decide not participate in the study, alternative treatments, no treatment (palliative care), etc.):** Patients who choose not to participate in this study will receive peripheral intravenous cannulation without the Buzzy® device.
2. **Describe the standard clinical care that may be an alternative:** Adult patients receive peripheral intravenous cannulation without any prophylaxis to the possible procedural pain, or they receive intradermal lidocaine injection prior to peripheral intravenous cannulation. N/A
3. **Describe how the subject can receive the research procedures/drug/device used in this study in a non-research setting:** Currently, the Buzzy® device is typically used on the pediatric population. Adults are not often offered the Buzzy® device, but, in certain hospitals, the Buzzy® device is also offered to adult patients. N/A

C. Objectives

1. **Describe the purpose, specific aims, or objectives of the study (i.e. the reason for performing the study in terms of the scientific question to be answered):**

Primary Aim: How much pain do adult patients experience with peripheral IV cannulation when Buzzy® device is used versus when intradermal lidocaine 2% is used?

Secondary Aim (1): How much satisfaction do adult patients experience with peripheral IV cannulation when Buzzy® device is used versus when intradermal lidocaine 2% is used?

Secondary Aim (2): How does first attempt during peripheral intravenous cannulation in adult patients compare when Buzzy® device is used versus when intradermal lidocaine 2% is used?

Secondary Aim (3): Does size of the peripheral intravenous catheter affect the pain that adult patients experience with peripheral IV cannulation?

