Secondary Aim (4): Does location of the peripheral intravenous catheter placement affect the pain that adult patients experience with peripheral IV cannulation?

D. Enrollment and Withdrawal

D.1 Inclusion Criteria

1. **Describe the criteria that define who will be included in the study as a numbered list:**

1. Adults ages 18 to 99
2. Non-pregnant women and men
3. Adults that are able to consent
4. Patients requiring intravenous catheter insertion for their operation/procedure

D.2 Exclusion Criteria

1. **Describe the criteria that define who will be excluded in the study as a numbered list:**

1. Patients with Raynaud's syndrome, sickle cell disease, and/or extreme sensitivity to cold
2. Patients with a break or an abrasion on the skin where the Buzzy device would be placed
3. Patients with nerve damage affecting the extremity where the peripheral intravenous catheter would be placed

2. **Describe in detail how the eligibility criteria will be assessed and satisfied (e.g., medical record review, physical examination):** Based on the pre-operative history and physical exam performed by the CA-1 (PGY-2) anesthesiology resident (co-investigator of study).
3. **State who will determine eligibility. Note that those who are designated to determine eligibility must have appropriate training, expertise, and oversight, for example a physician PI or Co-I on a biomedical**

study: PI (anesthesiology attending) and Co-I (CA-1 (PGY-2) anesthesiology resident). These will be the physicians who will be taking care of these subjects.

4. **Can study subjects participate in another research study while participating in this research study:**
 Yes No

D.3 Withdrawal of Subjects

1. **Describe anticipated circumstances under which subjects will be withdrawn from the research without their consent:** None
2. **Describe procedures that will be followed when subjects withdraw or are withdrawn from the research, including the possibility of partial withdrawal from study intervention with continued data collection:**
There will be no partial withdrawal from the study. Either the patient will take part in the study, which is just for the duration of the peripheral intravenous catheter insertion and the questionnaire that will take place before and after the procedure, or the patient will not take part in the study.
3. **Describe any necessary safety precautions to be applied to subjects who withdraw or are withdrawn (tapering drug doses, evaluative x-ray, etc.):** or N/A

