QUESTIONNAIRE

[figure not shown]
Questions to be answered by the Research Team:

Buzzy vs Intradermal Lidocaine for Peripheral Intravenous Cannulation in Adults

QUESTIONNAIRE

Questions to be answered by the Patient:

1) Please circle a number 0 to 10 in regard to how painful was the IV placement?

2) Please circle how satisfied you are with the IV placement?

Very Dissatisfied	Dissatisfied	Neither Satisfied nor Dissatisfied	Satisfied	Very Satisfied
(1)	(2)	(3)	(4)	(5)
				

2. *Is there a placebo control arm?*

Yes No

1. *Describe the following concerning pregnancy testing and birth control:*

- a. *What type of pregnancy testing and how frequently will be conducted on women of reproductive potential. If testing will not be conducted provide the reason:* N/A
- b. *What birth control methods women of reproductive potential will be instructed to use. If women will not be instructed about acceptable methods of birth control, clarify why:* N/A
- c. *What birth control methods men of reproductive potential will be instructed to use. If men will not be instructed about acceptable methods of birth control, clarify why:* N/A

2. *Describe the data that will be collected during the study and how the data will be obtained:*

- a. *If there are plans for long-term follow-up (once all research related procedures are complete), describe the data will be collected during this period:* or N/A

3. *Specify which procedures, tests, visits, etc. described above are part of usual standard of care at Tufts and which are performed solely for research purposes:* Insertion of intravenous catheter is part of the usual standard of care. The use of the Buzzy® device is not part of the current standard of care in adult patients at SEMC.

4. *Specify which tests are routinely performed for clinical care, but are providing data for the research, and which tests are only performed for research purposes:* No tests will be performed for the purposes of this study.

5. *For Humanitarian Use Device (HUD) uses provide a description of the device, a summary of how you propose to use the device, including a description of any screening procedures, the HUD procedure, and any patient follow-up visits, tests or procedures.* or N/A

F.3 Evaluations

Will you perform any laboratory tests for this study?

Yes No

F.4 Collection and Storage of Human Biological Specimens (Tissue Banking)

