2. *Include specific details of reporting procedures for:*
 - a. Deaths, life-threatening events, pregnancies: N/A
 - b. Other SAEs: N/A
 - c. Other AEs: N/A
 - d. Other UPS: N/A

H.3 Reportable New Information

Check to confirm that reportable new information will be reported to the IRB per the Tufts Health Sciences IRB's [Reportable New Information policy](#). If your reporting plan to the IRB differs from the IRB's policies, please describe it in detail or specify where this information is in the protocol:

I. Statistical Considerations

I.1 Study Endpoints

1. *Describe the primary and secondary study endpoints:* Primary study endpoint: Pain rating of the peripheral intravenous catheter insertion; Secondary study endpoint: Satisfaction rating of the peripheral intravenous catheter insertion
2. *Describe any primary or secondary safety endpoints:* N/A

I.2 Statistical Analysis

1. *Describe the statistical analyses that will be performed for this study:* Continuous variables will be analyzed via the Student's t-test and presented as mean +/- standard deviation. Categorical data will be analyzed via Chi-square test and presented as number and percentages. The intention-to-treat analysis will be used in this study. A P-value <0.05 will be considered statistically significant.
2. *Provide a power analysis:* Since there is currently no published study available comparing the two interventions that we plan on studying, we chose the study sample size based on the sample size rule of thumb for medical trials.¹³ The purpose of this study is to conduct a preliminary pilot trial for a potential future main trial designed with 90% power and two-sided 5% significance.

I.3 Number of Subjects

1. *Specify the number of subjects to be enrolled in total across all sites:* or N/A this is not a multicenter study.
2. *Specify the number of subjects to be enrolled at the Tufts site. Subjects who sign an ICF are considered “enrolled”. For studies that have a separate screening ICF, this number is the number of subjects who sign a screening ICF:* The goal will be to have a total of 30 subjects sign an ICF and complete the study based on the previously published sample size rule of thumb for medical trials.¹³

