 - a. *Provide the rationale for enrolling this number of subjects at the Tufts site:* Although unlikely, subjects might sign ICF and then change their mind within a few minutes while the research team member is preparing to perform the peripheral intravenous catheter insertion. To ensure we have 30 subjects complete the study, we will enroll up to 40 subjects in this trial.
 - b. *Estimate the number of subjects expected to be enrolled at the Tufts site (i.e. sign the screening or study ICF) as well as the number needed to complete the study at the Tufts site:* Subjects will only be enrolled in the study for the duration of the peripheral intravenous catheter insertion procedure and the time it takes to answer the questionnaire; therefore, in theory, only one or two subjects will be enrolled at the same moment.
 - c. *If a large number of withdrawals and/or dropouts is expected, explain why:* N/A

I.4 Data Management

1. *Describe the data analysis plan, including descriptions of the data:* The only data that will be collected is what is described in the questionnaire above.
2. *Provide a power analysis:* As described above, since there is currently no published study available comparing the two interventions that we plan on studying, we chose the study sample size based on the sample size rule of thumb for medical trials.¹³ The purpose of this study is to conduct a preliminary pilot trial for a potential future main trial designed with 90% power and two-sided 5% significance.
3. *Describe the steps that will be taken to secure the data (e.g., training, authorization of access, password protection, encryption, physical controls, certificates of confidentiality, and separation of identifiers and data) during storage, use, and transmission:* Data will be collected in an envelope and stored in a locked cabinet in the PI's office. Only the research team members will have access to the data for analysis purposes. Data will not have subject identifying information on it.
4. *Describe any procedures that will be used for quality control of collected data:* Data entry will be confirmed by two research team members.
5. *Describe how data and specimens will be handled study-wide as follows:*
 - a. *What information will be included in that data or associated with the specimens:* Please see section “F.2 Procedures” for the data that will be collected. No specimens will be collected.

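### Secondary Aims 3 and 4 (pain by catheter size and by site) have no planned method that can include treatment arm

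*Combined protocol and SAP*

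**What the plan says.** Section C sets two secondary aims on pain that do not mention arm. Aim 3: "Does size of the peripheral intravenous catheter affect the pain that adult patients experience with peripheral IV cannulation". Aim 4: "Does location of the peripheral intravenous catheter placement affect the pain that adult patients experience with peripheral IV cannulation".

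Section I.2 names two tests and ties neither to an aim. For continuous data: "Continuous variables will be analyzed via the Student's t-test and presented as mean +/- standard deviation". For categorical data: "Categorical data will be analyzed via Chi-square test and presented as number and percentages". It adds intention-to-treat and a 0.05 threshold. Section I.4, where a data analysis plan is requested, answers only on data content: "The only data that will be collected is what is described in the questionnaire above". Section F.2 says who will run and check the analysis, not how. No regression, analysis of variance, stratification or covariate appears in any of these places.

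The same co-investigator gives the allocated technique and places the catheter (F.2). Size and site are not randomised. The part of the questionnaire completed by the research team is a figure that is not shown, so the recorded size and site categories cannot be seen.

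The patient's second item ("Please circle how satisfied you are with the IV placement") has five ordered answers printed with the scores 1 to 5. Section I.1 lists the secondary endpoint as "Satisfaction rating of the peripheral intravenous catheter insertion" and does not class it as continuous or categorical.

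**The concern.** Every subject contributes a pain score obtained under one of two techniques. When pain is compared between catheter sizes by a t-test, any difference between techniques stays in the residual variation and makes a real size effect harder to detect. This holds even with only two sizes or sites. If there are three or more, a t-test also gives no single overall test, and the plan names nothing in its place.

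A second mechanism is possible. The operator knows the arm when placing the catheter. If the choice of size or site drifted with arm, an unadjusted comparison would attribute part of the arm difference to size or site.

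What is at stake is the efficiency, and conditionally the interpretation, of two secondary aims. The arm comparison of pain (t-test) and first-attempt success (chi-square) are adequately covered by I.2.

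**Working it through.** **Inputs from the protocol.** 30 completers (I.3), 1:1 allocation (I.5), so 15 per arm; significance at 0.05 (I.2). The protocol gives no SD or effect size, so there is no planned power to reproduce. The 30 comes from a cited rule of thumb, and this point does not concern it.

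**Assumptions.** Two-sided test (two-sidedness is stated only for the future main trial), normal pain scores with SD 1 within arm and group, a true difference of 1 SD between two size (or site) groups of 15, and size independent of arm.

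**Without arm.** An arm effect of δ SD, with half the subjects in each arm, adds δ²/4 to the residual variance. The noncentrality is √(15 × 15 / 30) / √(1 + δ²/4) = 2.739 / √(1 + δ²/4), on 28 degrees of freedom.
- δ = 0: 2.739, power 75%.
- δ = 0.5: 2.739 / 1.031 = 2.657, power 73%.
- δ = 1: 2.739 / 1.118 = 2.449, power about 66% (65% by simulation, which allows for the finite sample).

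**With arm.** Arm effects of any size are removed. Under random allocation the average squared correlation between arm and size is 1/29, so the noncentrality is about 2.739 × √(1 − 1/29) = 2.691, on 27 degrees of freedom. Power is 74% at every δ.

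**Other layouts (simulation, overall F-test, group means 0 / 0.6 / 1.2 SD).** Power without / with arm:

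| Group sizes | δ = 0 | δ = 0.5 | δ = 1 |
|---|---|---|---|
| 10 / 10 / 10 | 61 / 60% | 59 / 60% | 52 / 60% |
| 4 / 18 / 8 | 39 / 38% | 37 / 37% | 31 / 38% |

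**Error rate.** With no size or site effect and allocation independent of it, the false-positive rate is about 5% with or without arm.

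**If size did depend on arm (hypothetical).** Suppose the larger size is used in 25% of one arm and 75% of the other, with an arm effect of 1 SD and no size effect. The larger-size group is then 25% from the first arm and the smaller-size group 75%, so the expected bias is (0.25 − 0.75) × 1 = −0.5 SD. Simulation gave −0.52 SD and a 24% false-positive rate. At 35% against 65% it gave −0.31 SD and 10%. With arm in the model the bias was about zero and the error 4 to 5% in both cases.

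**Trend or categories.** Arm is in the model and δ = 1 throughout.
- Means rising steadily, 10 / 10 / 10: linear trend 72%, F-test 60%.
- Only the middle level raised (0 / 1.2 / 0): trend about 3%, F-test 73%.
- 4 / 18 / 8, steady rise: unmerged trend 48 to 49%; after merging the 4 into the 18, 35 to 36%. The unmerged trend without arm has 41 to 42%, so merging loses more than the arm term gains.
- 3 / 12 / 12 / 3, means 0 / 0.4 / 0.8 / 1.2: categories 24% on four levels and 30% merged to 15 / 15; unmerged trend 39%. Here merging helps categories and harms a trend.

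**The case against.** The strongest reply is that the gain depends on an arm difference the documents do not predict. Section B.1 looks ahead to a non-inferiority trial, so similar pain in both arms is a reasonable planning case. There the arm term costs 1 to 2 points of power; at 0.5 SD it gains about 1. Aims 3 and 4 do not mention arm, and an unadjusted comparison answers them validly on average if size and site are unrelated to arm. This stands, and it is why the point is minor.

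Three stronger readings are tempting and are not supported.

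- *A reader might infer that the planned tests inflate the false-positive rate.* At an arm effect of 1 SD the rate reaches 13% when three sites of 10 split 8/2, 5/5 and 2/8 between the arms. A split that uneven or worse arises by chance in 3.4% of allocations. At 5/5 throughout the rate is 2.4%, and the average is 5%.
- *A reader might infer that size and site are confounded with arm.* No section says either is chosen by arm. The skin and nerve-damage exclusions in D.2, such as "Patients with a break or an abrasion on the skin where the Buzzy device would be placed", imply that an intended site is considered before allocation. They say nothing about size, and the operator is not blinded, so imbalance is possible but not shown.
- *A reader might infer that satisfaction will be tested by an unordered chi-square test.* With 15 per arm and an assumed 3/7/15/35/40% distribution, chi-square, Wilcoxon and t-test power would be 17%, 35% and 36% at an odds ratio of 3. But the plan does not commit to chi-square. The natural reading of a rating with printed scores is the t-test, which is sound.

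The argument about three or more levels also stays conditional, because the number of levels is not visible.

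**Conclusion.** The concern holds in a limited form. The plan gives Aims 3 and 4 no method that can hold arm, and adding one is nearly free. The benefit is about 9 points of power (65% to 74%) if the techniques differ by 1 SD in pain, about 1 point at 0.5 SD, and a loss of 1 to 2 points if they do not differ. It also protects against confounding should size or site turn out to differ by arm. All effect sizes, group sizes and distributions above are assumptions. Severity is minor: these are secondary aims of a 30-subject pilot, and the primary comparison, safety and sample size are unaffected. The wording on satisfaction needs only a clarification.

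**What to change.** Add two or three sentences to I.2:

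1. Analyse Aims 3 and 4 by linear models of pain on arm plus size, and on arm plus site, with one overall test per aim, and label the results exploratory.
2. Enter size as an ordered trend and do not merge its levels. Enter site as categories. Merge only sparse site levels (for example, fewer than 5 subjects), decided before pain is examined.
3. Code arm A/B in the analysis file, so that the analysts need not know which technique is which (I.5).
4. As a clarification, state that the 1-5 satisfaction rating is compared by the t-test on scores, or by the Wilcoxon rank-sum test, and keep chi-square for first-attempt success.

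No data are needed beyond arm and what the aims already require. The cost is one degree of freedom per model, about 1 to 2 points of power if arm has no effect. The trend for size can miss a pattern in which only a middle size differs.

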 - b. *Where and how data or specimens will be stored:* Data will be stored in a locked cabinet in the PI's office (as described above).
 - c. *How long the data or specimens will be stored:* Data will be stored at least until the results of the study will be published.
 - d. *Specify who will have access to the data or specimens:* The Research team will have access to the data.
 - e. *Specify who is responsible for receipt or transmission of the data or specimens:* The PI will be responsible for the receipt of the data.

- f. **Specify how data and specimens will be transported:** Data will be transported in a closed envelope from the preoperative area and to the PI's office, where it will be stored in a locked cabinet. If data will need to be transferred between research team members for statistical analysis purposes, the word [SECURE] will be included in the subject line of all emails.
- g. **Specify the plan for study data retention and storage (accounting for research team turnover):** Data will remain secure in the PI's office, in a locked cabinet.

I.5 Randomization

Will subjects be randomized?

Yes No

If Yes respond to all of the following:

1. **Describe the randomization procedures, including the ratio of subjects randomized to each study arm:** We will use <http://www.graphpad.com/quickcalcs/index.cfm> to generate a randomized sequence, with a ratio of subjects 1:1 in each arm. <https://www.ncbi.nlm.nih.gov/pmc/articles/PMC3136079/>
2. **Describe the blinding procedures:** The Co-I's that will be conducting the statistical analysis will be blinded to which study arm the subjects were assigned to. N/A the study will not be blinded.

J. Drugs or Devices

1. Will the research involve drugs?

Yes No

If Yes, respond to all of the following:

- a. **If the drug is investigational (has an IND) identify the holder of the IND:** The drug, Lidocaine 2%, is not an investigational drug. It is a commonly used drug that is widely available.
- b. **Describe your plans to store, handle, and administer study drugs so that they will be used only on subjects and be used only by authorized investigators** N/A - this drug is used throughout the hospital for many procedures.
- c. **Who on the research team, in addition to the Principal Investigator, will be accountable for drug(s):** The PI and the Co-Is have access to Lidocaine 2% when they are interacting with patients.

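### I.2 names the pooled-variance t-test for the pain score although the plan secures neither equal arms nor equal SDs; Welch's test is a near-free improvement (minor)

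*Combined protocol and SAP*

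**What the plan says.** - **Endpoint.** Section I.1 makes the pain rating the primary endpoint. The questionnaire in F.2 collects it as a single item: "Please circle a number 0 to 10 in regard to how painful was the IV placement".
- **Test.** I.2, item 1 assigns continuous variables to Student's "t-test and presented as mean +/- standard deviation". In ordinary use that name means the pooled-variance test. No version for unequal variances is mentioned. The rule for significance is "A P-value <0.05 will be considered statistically significant".
- **Sidedness.** I.2, item 2 mentions two-sided testing only for a "potential future main trial designed with 90% power and two-sided 5% significance". Two-sided testing is assumed below for the pilot.
- **Allocation.** I.5, item 1 says a web tool will be used "to generate a randomized sequence, with a ratio of subjects 1:1 in each arm". Blocking, list length and type of randomisation are not stated.
- **Numbers.** I.3, item 2 says "The goal will be to have a total of 30 subjects sign an ICF and complete the study". Item 2a adds: "To ensure we have 30 subjects complete the study, we will enroll up to 40 subjects in this trial". The reason given is that "subjects might sign ICF and then change their mind within a few minutes", which the plan considers unlikely.
- **SDs.** None is given for either arm. Section B.1 says no published study compares the two techniques in adults.

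**The concern.** The pooled test relies on equal SDs, equal arm sizes, or both. The plan secures neither.

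Arm sizes can differ for two reasons. An unrestricted 1:1 sequence need not be balanced at 30. A sequence balanced at 40 need not be balanced if recruitment ends once 30 have completed. SDs can differ because the score is bounded at 0, and one technique may work more consistently than the other.

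When both differ, the pooled standard error is wrong in a direction that depends on which arm is smaller. The P<0.05 rule for the main comparison then runs above or below 5%. The same pooling would distort the SD passed to the later non-inferiority trial, if a single pooled value were carried forward.

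**Working it through.** **Inputs.** From the documents: 30 completers, up to 40 enrolled, 1:1 ratio, Student's t-test, P<0.05. Assumed: two-sided test, normal data unless stated, SD ratio 1.5 to 2. The plan states no error rate beyond the nominal 5%. Its sample size of 30 comes from a cited rule of thumb whose inputs are not in the documents, so there is no figure to reproduce.

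**Step 1: why the pooled standard error goes wrong.** Set the smaller SD to 1 and the larger to r.

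- True variance of the mean difference: s1²/n1 + s2²/n2.
- Expected pooled estimate: [((n1−1)s1² + (n2−1)s2²)/28] × (1/n1 + 1/n2).

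| Split and r = 2 | True variance | Pooled estimate | Estimate/true |
|---|---|---|---|
| 15:15 | 4/15 + 1/15 = 0.333 | 2.500 × 0.1333 = 0.333 | 1.00 |
| 12:18, larger SD in the 12 | 4/12 + 1/18 = 0.389 | (44+17)/28 × 0.1389 = 0.303 | 0.78 |
| 12:18, larger SD in the 18 | 4/18 + 1/12 = 0.306 | (68+11)/28 × 0.1389 = 0.392 | 1.28 |

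At r = 1.5 the two 12:18 ratios are 0.85 and 1.17.

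**Step 2: error rate given the split.** Simulation with 200,000 normal trials per cell; repeat runs agree to about 0.1 percentage point.

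| Setting | Student | Welch |
|---|---|---|
| 15:15, r = 1.5 / 2 | 5.1% / 5.3% | about 5.0% |
| 12:18, smaller arm more variable, r = 1.5 / 2 | 7.0% / 8.6% | about 5.1% |
| 12:18, larger arm more variable, r = 1.5 / 2 | 3.6% / 3.0% | about 5.0% |
| 12:18, equal SDs | about 5.0% | about 5.0% |

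**Step 3: how likely the split is.**

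- Simple randomisation, Binomial(30, 0.5): P(12:18 or worse) = 0.362.
- Balanced list of 40 cut at 30, hypergeometric (40, 20, 30): P(12:18 or worse) = 0.065.
- Balanced list of 30 with no withdrawals: 15:15 exactly.

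**Step 4: average over splits.** Weighting the conditional error rates by these probabilities gives, for Student's test:

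- Simple randomisation: 5.3% (r = 1.5) and 5.7% (r = 2).
- Balanced list of 40 cut at 30: 5.2% and 5.3%.

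Allowing for simulation error, the range is about 5.1 to 5.7%.

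**Step 5: scores rather than normal data.** One assumed pair of 0-10 distributions had equal means and SDs of 2.57 and 1.31.

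| Setting | Student | Welch |
|---|---|---|
| 15:15 | 6.3% | 6.1% |
| 12:18, smaller arm more variable | 9.5% | 6.8% |
| 12:18, larger arm more variable | 3.9% | 5.5% |

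Other assumed floor-heavy scores (equal means of 1.5 to 3, SD ratios about 1.6 to 1.95), at 12:18 with the smaller arm more variable, gave Welch 5.9 to 10.5% and Student 7.9 to 11.6%.

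**Step 6: price of Welch's test when SDs are equal.** Power at a difference of one SD is 75.1% against 75.3% for Student at 15:15, and 72.9% against about 73.5% at 12:18.

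**Step 7: the SD carried forward.** At 12:18 the pooled variance is 2.179 or 2.821 when r = 2, against an average of 2.5 (−13% or +13%). At r = 1.5 it is 1.491 or 1.759 against 1.625 (−8% or +8%). If an equal-arm main trial were sized for 90% power from that single value, its power would be Φ(3.242 × √f − 1.960), where f is pooled variance divided by average variance. That is about 86 to 87% when f is 0.87 to 0.92, and 92 to 93% when f is 1.08 to 1.13.

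**The case against.** The strongest reply is that the harm is conditional and small. It needs an uneven split and unequal SDs together, and the errors in the two directions largely offset. A stated 1:1 ratio may well mean a balanced list, which makes 12:18 uncommon (6.5%). Nothing confirmatory rests on P<0.05 in a pilot meant to inform a later sample size. All of this stands, and it is why the point is minor.

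It is also fair to say that a technique that works better changes the mean as well as the SD, whereas type I error concerns equal means. If the two pain distributions were identical, the SDs would be equal and Student's test would hold 5% at any split. Unequal SDs at equal means are therefore possible but not shown. Nor is Welch's test exact on scores bunched at 0, as step 5 shows.

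Three stronger readings are tempting, and the documents do not support them:

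- **That the list has no blocks.** I.5 is silent on blocking, and silence does not show its absence.
- **That recruitment stops at 30.** This is a reasonable inference from I.3, but no stopping rule is written.
- **That the trial's error rate is 3 to 9%.** That range belongs to one scenario (12:18 with an SD ratio of 2) and is not the overall level.

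What survives is that a single trial has one split, known at analysis, and a named method can be replaced by a better one at almost no cost.

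**Conclusion.** The point holds as a minor one. I.2 names the pooled test with no alternative, and I.3 and I.5 do not secure equal arms. Given a 12:18 split and an SD ratio of 1.5 to 2, the nominal 5% becomes about 7 to 8.5% or about 3 to 3.7%, depending on which arm is the more variable. Averaged over splits it is about 5.1 to 5.7%. These figures rest on assumed SD ratios, normal data and a two-sided test. A reader might infer that the pain comparison is invalid as planned; that does not follow. The loss of precision is also slight: the variance factor (1/12 + 1/18)/(2/15) is 1.042, a 4% rise at 12:18. Whether the later trial's sample size is affected depends on how the SDs are carried forward, which the plan does not say.

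**What to change.** In I.2, item 1, replace Student's t-test with Welch's unequal-variance t-test for the comparison of arms. State that the SD will be reported for each arm separately and that both will be used when the later trial is sized. I.2 already presents means with SDs, so this adds no data collection. The cost is about 0.2 percentage points of power at 15:15 and 0.6 at 12:18 if the SDs are in fact equal.

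Optionally, state in I.5 the list length and whether blocks are used. If they are, mixed block sizes not disclosed to the residents who enrol would keep the arms near 1:1 wherever recruitment ends. The cost is some predictability near block ends, since the operators can see which technique each subject received. The main change does not depend on this one.
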